• To investigate the safety and efficacy of intravenous infusions of HB-adMSCs vs Placebo in patients with Parkinson's disease as determined by improvements in Quality of Life, estimated by the MDS UPDRS assessment. (Time frame: Baseline to Weeks 4, 8, 16, 24, 32, 42 and 52). A battery of statistical tests will be applied, where suitable and applicable. Tests will include the report of parametric or non-parametric statistical tests, with the corresponding p-values, presented in pair-wise manner, as well as contingency tables, representing answers in their native form.	 Change from Baseline in Total MDS-UPDRS Part II, only at Week 52 Number of treatment-emergent Adverse Event (TEAEs) during 52 week period Number of serious Adverse Events (SAEs) during the period of 52 weeks Number of AEs of special interest includes thromboembolic events, peripheral events defined as thromboembolism of the extremities, infections and hypersensitivities Change from baseline in clinical parameters, measured at the end of the study (52 weeks): Physical examination Electrocardiogram (ECG) Pulse Systolic blood pressure Body weight BMI Change from baseline in laboratory assessments at the end of the study (52 weeks):

Protocol Number: HBPD03

Date: 18-Apr-2023 Version: 2.0 Hope Biosciences Statistical Analysis Plan Status: Final

Objectives	Endpoints
	o Biochemistry
	 Haematology
	 Urinalysis
Secondary Objectives	Secondary Endpoints
To evaluate the safety and efficacy of intravenous infusions of HB-adMSCs vs Placebo in patients with Parkinson's disease based on	Change from Baseline in MDS- UPDRS Total score, at all the timepoints collected, during the period of study (52 Weeks)
changes in disease assessments and dosage of medications. (Time frame: Baseline to Weeks 4, 8, 16, 24, 32, 42 and 52).	 Change from Baseline in Total MDS- UPDRS Part I, at all the timepoints collected during the period of study (52 Weeks)
	 Change from Baseline in Total MDS- UPDRS Part II, at all the timepoints collected during the period of study (52 Weeks)
	 Change from Baseline in Total MDS- UPDRS Part III at all the timepoints collected during the period of study (52 Weeks)
	 Change from Baseline in Total MDS- UPDRS Part IV, at all the timepoints collected during the period of study (52 Weeks)
	 Change from Baseline in Total Neuro- Quality of Life Assessments scores (Neuro-QOL), at all the timepoints collected during the period of study (52 Weeks)
	• Change from Baseline in Total Parkinson's disease fatigue scale (PFS-16), at all the timepoints collected during the period of study (52 Weeks)
	Change from Baseline in Total Parkinson's disease Questionnaire (PDQ-39), at all the timepoints

Confidential

Protocol Number: HBPD03 Hope Biosciences Statistical Analysis Plan Date: 18-Apr-2023 Version: 2.0 Status: Final

Objectives	Endpoints
	collected during the period of study (52 Weeks)
	• Change from baseline in Total VAS score
	• Change from baseline in Muscle Spasm Scale VAS score at Week 52
	• Change from baseline in Pain Scale VAS score at Week 52
	 Number of subjects with changes in Daily Dosage of medications taken to treat Parkinson's disease at all the time point during the period of 52 weeks
	 Proportion of subjects requiring reinstatement of PD medication dose following reduction in dose during the study

Confidential

Protocol Number: HBPD03 Hope Biosciences Statistical Analysis Plan Date: 18-Apr-2023 Version: 2.0 Status: Final

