	Placebo: Saline Solution 0.9%						
	Dose: N/A						
	Route: Intravenous						
	Regimen: Weeks 0, 4, 8, 16, 24 and 32.						
Duration of administration	1 hour						
Laboratory Samples.	Screening, Week 0, 24 and 52.						
Visits by Weeks	Screening						
	Week 0 – Infusion 1						
	Week 4 – Infusion 2						
	Week 8 – Infusion 3						
	Week 16 – Infusion 4						
	Week 24 – Infusion 5						
	Week 32 – Infusion 6						
	Week 42 – Follow Up.						
	Week 52 – End of Study						

"A Randomized, Double-Blind, Single Center, Phase 2, Efficacy and Safety Study of autologous HB-adMSCs vs Placebo for the Treatment of Patients with Parkinson's Disease"

Introduction

Objectives

Primary Objective:

• To investigate the safety and efficacy of intravenous infusions of HB-adMSCs vs Placebo in patients with Parkinson's disease as determined by improvements in Quality of Life as measured by the MDS UPDRS assessment. (Time frame: Baseline to Weeks 4, 8, 16, 24, 32, 42 and 52).

Secondary Objective:

• To evaluate the safety and efficacy of intravenous infusions of HB-adMSCs vs Placebo in patients with Parkinson's disease as, determined by changes in disease assessments and dosage of medications. (Time frame: Baseline to Weeks 4, 8, 16, 24, 32, 42 and 52).

Endpoints

Primary Endpoints

The safety and efficacy endpoints of this study will be evaluated by assessing changes from Baseline to Weeks 52 in the following:

- Changes in MDS-UPDRS Part II from Baseline to Week 52. Motor Aspects of Experiences of Daily Living (M-EDL), including speech, saliva and drooling, chewing and swallowing, eating tasks, dressing, hygiene, handwriting, doing hobbies and other activities, turning in bed, tremor, getting out of bed, a car, or a deep chair, walking and balance and freezing.
- Incidence of treatment-emergent Adverse Event (TEAEs) and serious Adverse Events (SAEs).
- Incidence and risk of AEs of special interest (serious or nonserious), including thromboembolic events, peripheral events defined as, thromboembolism of the extremities, also infections and hypersensitivities.
- Clinically significant changes in laboratory values, vital signs, weight and physical examination results.

Secondary Endpoints

The safety and efficacy endpoints of this study will be evaluated by identifying changes from Baseline to Weeks 4, 8, 16, 24, 32, 42 and 52 in the following:

- Changes in MDS-UPDS Part I, III, IV, or total score.

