8.1. Adverse Events Analyses

AEs will be coded using the most recent version of the Medical Dictionary for Regulatory Activities (MedDRA).

A treatment emergent adverse event (TEAE) is defined as an event that has onset date on the first day of exposure or after the first day of exposure to infusion treatment, and no later than 3 days after the last day of infusion treatment. AEs with missing start and/or stop dates will be assumed to be treatment emergent.

Treatment adverse events (TAE) are summarised descriptively, whereas non-TEAEs are presented in listings. TAE data will be displayed in terms of the number of subjects with at least one event (N), percentage of subjects with at least one event (%) and the number of events E.

Summaries of TAE and of serious AEs will be presented as an overview, including all AEs, AEs listed by severity, serious AEs, AEs by relation to treatment, action taken after AEs occurred and treatment advised, and the outcome of AEs.

Furthermore, summary tables based on system organ class and preferred terms are made for:

- All TAEs
- Serious AEs
- AEs leading to withdrawal of study

Individual adverse events will be listed.

The details of the planned displays are in Error! Reference source not found..

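### The SAP replaces the protocol's incidence and risk of adverse events of special interest with a number of events, and section 8.1 pre-specifies no grouped by-arm summary or time window for this primary safety endpoint

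*SAP*

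**What the plan says.** The protocol, under Primary Endpoints, lists "Incidence and risk of AEs of special interest (serious or nonserious), including thromboembolic events", and names thromboembolism of the extremities, infections and hypersensitivities with it. The same item is repeated under Secondary Endpoints.

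The SAP's table of objectives and endpoints gives the matching primary endpoint as "Number of AEs of special interest includes thromboembolic events, peripheral events defined as thromboembolism of the extremities, infections and hypersensitivities". The lines beside it for treatment-emergent and serious adverse events state a 52-week period; this line states none.

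SAP 8.1 sets out the adverse event analysis:
- Treatment adverse events are described by the "number of subjects with at least one event (N), percentage of subjects with at least one event (%) and the number of events E".
- An overview covers all adverse events and "AEs listed by severity, serious AEs, AEs by relation to treatment, action taken after AEs occurred and treatment advised, and the outcome of AEs".
- Next, "summary tables based on system organ class and preferred terms are made for" three categories: all treatment adverse events, serious adverse events, and adverse events leading to withdrawal.
- "Individual adverse events will be listed".
- "The details of the planned displays are in" a place that the text does not identify, because the cross-reference has failed.

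SAP 8.1 also defines an event as treatment-emergent only up to 3 days after the last infusion, and sends other events to listings. The protocol, under Adverse Event Reporting Period, follows patients for about 20 weeks after the last administration.

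**The concern.** Incidence and risk need a denominator; a number of events has none. The SAP therefore changes what is measured for a primary endpoint, and the section that should analyse it does not mention it.

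The general tables do not fill the gap. Thromboembolism and hypersensitivity can each be coded to several preferred terms, and one patient can appear in several rows. The number of patients with at least one event in the group cannot be obtained by adding rows. Infections may be readable from one organ class.

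These are the risks that the protocol singled out; thromboembolic events also appear in its Study Stopping Rules. If the SAP is followed as written, the report need contain no by-arm, patient-level result for them. A grouping made later from the listings would be chosen with the results in view. Under SAP 5.5, subject-level data are unblinded at the interim analysis and results go to members of the sponsor.

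**Working it through.** The documents give no AESI rate, effect size or power, so there is no figure of the plan to reproduce. The check is a comparison of texts, followed by three short calculations.

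**1. Side by side**

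| Element | Protocol, Primary Endpoints | SAP endpoint table | SAP 8.1 |
|---|---|---|---|
| Measure | Incidence and risk | Number of events | Patients, % and events, for treatment adverse events in general |
| Unit | Not stated | Events | Patients and events |
| AESI group | Named | Named | Not among the overview categories or the 3 tables |
| Period | To Week 52 (lead-in sentence) | Not stated on this line | Treatment-emergent: to 3 days after last infusion |
| Risk estimate by arm | Implied by risk | None | None |

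No other part of the supplied SAP gives an AESI term list, grouping rule or by-arm risk estimate.

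**2. Time window**

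Inputs: last infusion at Week 32, end of study at Week 52 (both documents); 3-day limit (SAP 8.1).
- The window closes at 32 × 7 + 3 = 227 days.
- The study lasts 52 × 7 = 364 days.
- Days outside the window: 364 − 227 = 137, and 137 / 364 = 38%.

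Under the general rule in 8.1, an AESI in those 137 days goes to a listing. The serious-event and withdrawal tables are not expressly limited to treatment-emergent events, so late events of those kinds might be tabulated there. Late non-serious events that do not lead to withdrawal would not be.

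**3. Can the count and the incidence disagree?**

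Input: 12 patients per arm (protocol, randomisation section).

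An example: 5 events in each arm is a tie on the SAP's measure. If they fall in 1 patient in one arm and 5 patients in the other, the incidence is 1/12 = 8% against 5/12 = 42% (two-sided Fisher p = 0.155).

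How often this happens depends on the event rate, which the documents do not give. Assume negative binomial counts with shape 0.5 to 1 and no true difference between arms. The share of trials in which the two measures point to opposite arms is:

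| Assumed mean events per patient | Opposite arms |
|---|---|
| 0.5 to 1 | about 7% to 15% |
| 0.1 to 0.2 | at most about 2% |

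At 0.5 to 1 event per patient, trials in which one arm has more events but not more affected patients come to about 21% to 30%. That figure includes ties on patients, so it does not measure reversal.

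**4. Why an interval belongs in the table**

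With 0 of 12 patients affected, the exact two-sided 95% upper limit is 1 − 0.025^(1/12) = 26.5%. This follows from the arm size and not from the SAP's wording. It shows how little an empty row would exclude.

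**The case against.** The strongest reply is that SAP 8.1 already plans patient-level reporting: patients and percentages stand beside the event count, SAP 5.1 sets the comparison as active against placebo, and every event is listed. With 24 patients, anyone could count those with a thromboembolic event. This stands as far as it goes. A reader might infer that the arms cannot be compared on AESI; the documents do not support that. What is missing is a grouping fixed in advance.

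A reader might also see three competing definitions of one endpoint. That goes too far. The protocol gives no unit, so patient-level incidence is the natural reading but not a stated one, and 8.1 omits the group without redefining the endpoint. There is one change of wording and one omission.

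An AESI table might exist in the display list behind the broken reference. This can be neither confirmed nor excluded. It would not cure the endpoint wording, and the text of 8.1 itemises its tables without one.

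It is also tempting to say that counting events inflates false-positive findings. The SAP plans no test of AESI: treatment adverse events are summarised descriptively, and the formal hypothesis in SAP 2.3 concerns efficacy. No error rate of the plan is affected.

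Finally, repeated events are most plausible for infections, which may be readable from one organ class. For rarer groups the count and the incidence will seldom disagree. That limits the size of the problem, as the low-rate row in the second table shows.

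**Conclusion.** The point holds as a mismatch plus an omission. The protocol's incidence and risk endpoint becomes a number of events in the SAP, without denominator, risk measure or period, and the text of 8.1 defines no analysis for it. The comparison remains possible after the fact, but it is not pre-specified.

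The firmest figure is the window: about 38% of the 52 weeks lies outside the treatment-emergent period, assuming the last infusion is on schedule at Week 32. The chance that the count and the incidence favour opposite arms is about 7% to 15% at 0.5 to 1 event per patient and at most about 2% at 0.1 to 0.2. Both ranges rest on assumed rates and an assumed negative binomial model. The sponsor should make the change, because the endpoint is primary and the correction is nearly free. The efficacy conclusion does not depend on it.

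**What to change.** 1. In the SAP endpoint table, state the endpoint as the number and percentage of patients with at least one AESI, serious or not, over the 52-week period, with the number of events as support.
2. In SAP 8.1, add one by-arm table on the Safety analysis set. Rows: thromboembolic events (extremity events as a sub-row), infections, hypersensitivities, and any AESI. Count each patient once per row.
3. State that this table covers all events from first infusion to Week 52, whatever the treatment-emergent flag.
4. Give an exact 95% confidence interval for the incidence in each arm and an interval for the risk difference. No test is needed.
5. Fix the preferred-term list for each row before any unblinding, including the interim analysis; if that has already taken place, record when the list was fixed and by whom in terms of role and blinding.
6. Repair the cross-reference to the planned displays, and list the new table there.

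The cost is SAP wording, one table and a term list drawn up blind. The data are already collected under the protocol.

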2.2. Study Design

Overview of	Study Design and Key Features
Randomized,	double-blind, placebo-controlled, parallel group study
Design Features	 Randomized, double-blind, Placebo controlled, parallel group study. 24 Subjects 2 Treatment groups Group 1 → HB-adMSCs Group 2 → Placebo Duration of treatment: up to 32 weeks. The overall study includes screening (up to 4 weeks prior to randomisation), 6 treatment visits after randomisation scheduled according to the following schedule: Infusion 1 (Week 0), Infusion 2 (Week 4), Infusion 3 (Week 8), Infusion 4 (Week 16), Infusion 5 (Week 24) and Infusion 6 (Week 32). After all the treatments were administered to the patients, there will be two follow up visits, the first one the Week of 42, and the second one, at the end of study, at Week 52.
Dosing	 HB-adMSCs (Hope Biosciences adipose derived mesenchymal stem cells) will be administered as an IV infusion with the dose of 200 million cells Placebo is to be administered as an IV infusion which contains saline solution (0.9%)
Treatment Assignment	Participants will be randomised in 1:1 ratio, to receive either HB-adMSCs active treatment or Placebo.

2.3. Statistical Hypotheses

The null hypothesis states that there is no significant difference in primary efficacy endpoint, Change from Baseline in the total MDS-UPDRS Part II score, compared to the value at Week 52, between the HB-adMSCs and Placebo treatment groups. The alternative hypothesis is that there is a significant difference between the HB-adMSCs and Placebo treatment groups, meaning that the treatment was effective. The hypothesis will be tested using 5% significance level (two-sided).

All other secondary endpoints are tested as exploratory analysis. The criteria will be the same as for the primary endpoint, 5% significance level, two-sided tests, which is a standard in biology and medicine.

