- 4. Principal Investigator may stop the infusion at any time, based upon PI's discretion.
- 5. Malignant Hypertension (180/120 mm/Hg)

Confidential

6. Sudden Severe Hypotension (30-40 mm/Hg drop from pre-infusion level)

If an infusion is stopped for a subject due to an adverse event or serious adverse event, including but not limited to hypersensitivity reaction/anaphylaxis, no additional study treatment will be given to the study participant who develops the event. Although, the study participant will not receive the investigational product, he or she must be followed for safety purposes according to the protocol.

Study Stopping Rules

This Clinical Trial will stop if any of the following events are present:

- 1. Subject's Death.
- 2. Occurrence of any thromboembolic event during or after HB-adMSCs administrations (up to 72 hours).
- 3. Any cerebrovascular ischemia or seizure event occurring within 72 hours after any of the investigational product administrations.
- 4. Any Serious Adverse Events determined to be related to the following:
 - When there is one CTCAE.v5 grade 4 or 5 AE, irrespective of attribution.
 - Either any CTCAE Grade 2 adverse event that persists for more than two weeks, or any Grade 3 adverse event, that occurs within 72 hours after product administration.

Should the study participant discontinue study treatment he/she will be followed for safety according to the protocol safety monitoring plan. The study participant will receive follow up communication to ascertain the outcome until resolved fully. All will be documented as per protocol.

Statistical Methods

Sample size consists of up to 24 subjects who have been diagnosed with Parkinson's disease. All data collected from subjects who are enrolled and received the investigational product will be analyzed. The incidence of Adverse Events and Serious Adverse Events will be recorded and reported. Efficacy will be measured by improvement of subject's signs and symptoms associated with Parkinson's disease. Interim analysis of all safety and efficacy data may be performed at any time deemed appropriate by the Sponsor. Although, the subject's data may be analyzed at any time, a data analysis of all available data will be conducted when a least 10 subjects in each group have completed Week 24. Data may be analyzed for internal informational purposes, reports, presentations, and manuscripts.

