5.2.1 Change from Baseline

Definition	Reporting Details
Change from Baseline	= Post-Dose Visit Value – Baseline
% Change from Baseline	= 100 x [(Post-Dose Visit Value – Baseline) / Baseline]

NOTES:

• The baseline will be displayed along with Visit name on all summary displays.

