5.6 General Considerations

Unless otherwise stated, all hypotheses will be tested at 0.95% confidence interval (p = 0.05, two-sided test, when applicable). In other words, statistical test will look for the difference (either better results or worse results), rather than focusing solely on efficacy. All continuous measurements will be summarised descriptively at each visit, followed by treatment, using observed data.

Summary of continuous variables will be presented using the total number of participants (N), Mean, Standard Error of mean (SE), Standard Deviation (SD), Median and Range (Minimum and Maximum). The categorical variables will be presented using the number and the percentage of subjects who have provided the defined categorical answer.

For measurements obtained during course of time, mean values will be plotted to explore the trends. Observed data will be used as the basis for plotting data along with standard error (SE) or Standard Deviation (SD) represented as bars, if not otherwise specified.

A non-parametric Mann-Whitney U Test (or Wilcoxon Rank-Sum Test) will be applied on primary and secondary efficacy endpoints to test the significance of the effects of the treatment by comparing median values.

For measurements performed over time, median values will be plotted to explore the trends. Observed data will be used as the basis for plotting the data along with Inter Quartile Range (IQR) used as bars, if not otherwise specified.

A parametric, repeated measurements ANOVA will be applied as a sensitive analysis to test the significance of the effects of the treatment.

Change from baseline safety Lab measurements will be analyzed using a repeated measurements ANOVA to test the significance of the effects of the treatment.

Presentation of results from a statistical analysis model will include the estimated means caused by treatment effects, using Adjusted Mean. HB-adMSCs 200MM vs Placebo group will be compared.

For all endpoints analyzed statistically, estimated mean treatment differences will be presented together with two-sided 95% confidence intervals and p-values.

All safety evaluations will be presented using Safety analysis set while the efficacy analysis

Individual safety and efficacy parameters will be listed.

will be presented using Efficacy analysis set.

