7. EFFICACY ANALYSES

7.1. Primary Efficacy Analyses

7.1.1. Endpoint / Variables

The primary efficacy endpoint is difference between the Baseline value in Total MDS-UPDRS Part II score and the value measured at the end of the study (Week 52).

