7.1.4.1. Statistical Methodology Specification

Primary endpoint will be analyzed using the Mann-Whitney U Test (or Wilcoxon Rank-Sum Test) for the comparison of HB-adMSCs 200MM vs. Placebo.

Sensitivity analysis

Sensitivity analysis will be performed on Efficacy analysis set using a repeated measurements ANOVA model to evaluate the robustness of using parametric method. If the normality of dataset shows significant violation from the presumption of normality, the parametric method will not be performed.

All primary endpoint efficacy measurements available at post-baseline at scheduled measurements will be analyzed using Repeated Measures ANOVA. The model will include treatment, visits as fixed factors. The within subject factor is visit and with 7 levels (Weeks 4, 8, 16, 24, 32, 42 and 52). The between-subjects factor is treatment (HB-adMSCs 200MM or Placebo).

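### SAP 2.3 reads any significant two-sided difference on the primary endpoint as effectiveness, which conflicts with SAP 5.6 and leaves the direction of benefit unstated

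*SAP*

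**What the plan says.** SAP 2.3 (Statistical Hypotheses) sets a null of no difference between arms in the change in Part II at Week 52. Its alternative is that "there is a significant difference between the HB-adMSCs and Placebo treatment groups, meaning that the treatment was effective". The level is 5%, two-sided.

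SAP 5.6 (General Considerations) describes the same kind of test differently: "statistical test will look for the difference (either better results or worse results), rather than focusing solely on efficacy".

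Four other places bear on direction:

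- SAP 7.1.1, for Week 52: "The primary efficacy endpoint is difference between the Baseline value in Total MDS-UPDRS Part II score and the value measured at the end". This does not say which value is subtracted from which.
- SAP 5.2.1: change from baseline is "Post-Dose Visit Value – Baseline". This fixes the arithmetic but does not say which sign is benefit.
- SAP 7.1.4.1: "Primary endpoint will be analyzed using the Mann-Whitney U Test (or Wilcoxon Rank-Sum Test) for the comparison of HB-adMSCs 200MM vs. Placebo". It names the test and gives no rule for reading the result.
- Objectives: the SAP's primary objective speaks of efficacy "as determined by improvements in Quality of Life, estimated by the MDS UPDRS assessment", and the protocol's Statistical Methods section says "Efficacy will be measured by improvement of subject's signs and symptoms associated with Parkinson's disease".

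**The concern.** A two-sided test can reject in either direction. If rejection is defined in advance as effectiveness, a trial in which Part II worsens significantly more on HB-adMSCs than on placebo meets the written criterion. The plan then gives the wrong conclusion for every rejection in the harmful tail, and it has no stated conclusion for harm on the primary endpoint. SAP 5.6 accepts that a significant difference may mean worse results, so the SAP disagrees with itself on what rejection means.

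**Working it through.** **The text side by side.** Under 2.3, rejection means effective. Under 5.6, rejection means better or worse. Both cannot hold. The references to improvement in the objectives show the intended direction, but they do not settle the matter between arms: both arms could improve, with placebo improving more. SAP 5.2.1 gives the sign of the subtraction and nothing gives the sign of benefit. The nearest guide is the protocol's randomization section, which places higher MDS-UPDRS scores in the moderate rather than the mild stratum, so a lower score is the better one. That section does not name Part II, so this is an inference.

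**Inputs.** 12 subjects per arm (protocol, Investigational Product Assignment); Mann-Whitney test (SAP 7.1.4.1); 5% two-sided (SAP 2.3). The documents give no power, effect size or SD, so there is no figure of theirs to reproduce. The effects below are assumptions.

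**No true effect, exact, no ties.** Let U be the number of the 12 × 12 = 144 between-arm pairs in which the HB-adMSCs subject has the higher (worse) change.

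- The largest critical region within 2.5% per tail is U ≤ 37 or U ≥ 144 − 37 = 107.
- P(U ≥ 107) = 60,711 / 2,704,156 = 2.25%, where the denominator is the number of ways to choose 12 from 24.
- Both tails together: 2 × 2.245% = 4.49%.

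Under the literal wording, the chance of a false conclusion of effectiveness is 4.49%, and half of it comes from results favouring placebo. With a direction added it is 2.25%. The test is the same in both cases.

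**Assumed true harm.** The table gives the chance of a significant result favouring placebo, with 12 per arm and normal data. The second column is simulated with 40,000 trials; repeat runs agree to about 0.3 percentage points. The third is a hand check for two means, 1 − Φ(1.96 − d/√(2/12)). At d = 0.5 this is 1 − Φ(1.96 − 1.225) = 23.1%. It runs higher because it treats the SD as known and compares means rather than ranks.

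| Assumed harm (SD) | Mann-Whitney | Normal approximation, two means |
|---|---|---|
| 0.25 | 7.6% | 8.9% |
| 0.5 | 19.5% | 23.1% |
| 1.0 | 60.5% | 68.8% |

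**Sensitivity at 0.5 SD.** SAP section 4 limits the efficacy set to subjects with all six infusions, and SAP 10.1.2.1 excludes subjects with missing data, so 12 per arm is the maximum. At 10 per arm the figure is about 16%. SAP 5.4 puts Part II at Week 52 in a Holm procedure over eight endpoints that starts at 2.5%/8 = 0.31%. At that level, with 12 per arm, the figure is about 3%.

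**The case against.** The strongest reply is that this is loose wording which nobody would act on. The objectives and the protocol tie efficacy to improvement, and SAP 5.6 requires estimated treatment differences with two-sided 95% confidence intervals. Any report would show the direction, and a result favouring placebo could hardly pass as efficacy. This stands, and it keeps the practical impact low. It does not remove the contradiction, because the section that states the hypothesis still gives the wrong meaning to half of the rejection region.

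Four stronger readings are tempting, and the documents do not support them:

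- *The effectiveness criterion also governs the secondary endpoints.* The sentence in 2.3 that extends the criteria goes on to name them: the 5% level and two-sided testing. It does not carry over the meaning of rejection, and it calls those tests exploratory.
- *The sign of the change is undefined.* SAP 5.2.1 defines it. Only the sign that means benefit is missing.
- *SAP 2.3 is the only written rule for a conclusion.* SAP 5.4 sets a Holm procedure for conclusions that includes Part II at Week 52. It gives no direction either.
- *The stakes are higher because this is the product's first controlled comparison.* The documents do not say so.

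**Conclusion.** The point holds as a wording defect in the decision rule for the primary endpoint. SAP 2.3 and 5.6 conflict on what a significant result means, and no between-arm directional criterion was found to resolve it. An early part of the SAP was not available, so this rests on the remaining text.

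In size, the literal rule mislabels 2.25% of trials under no effect, and about 7.6% to 60.5% under assumed harm of 0.25 to 1.0 SD. Those figures assume 12 analysed per arm, an unadjusted 5% level and no ties; the harm figures also assume normal data. They fall with fewer subjects or under the Holm levels. They describe what the sentence permits. They do not predict what the sponsor would report, and they do not show that the two-sided test is unsound.

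**What to change.** In SAP 2.3:

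1. Delete the closing clause that equates a significant difference with effectiveness, and state the alternative as a difference in either direction.
2. Add that efficacy is concluded only if the two-sided test is significant at the level the SAP applies and the Part II change (Week 52 minus baseline) is lower on HB-adMSCs than on placebo, with direction read from the rank-sum statistic itself. A significant difference the other way is reported as worsening.

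In SAP 7.1.1, word the endpoint as Week 52 minus baseline, to match 5.2.1.

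The cost is about two sentences in 2.3 and a phrase in 7.1.1. The test, alpha, p-value, sample size and data collection do not change. Which level applies, the 5% of 2.3 or the Holm levels of 5.4, is a separate question that this change does not settle.
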